8.3.2 Inclusion Criteria

To be eligible for study entry subjects in **Cohort 1** (previously completed the treatment period in protocol ND0612H-006 within one month prior to enrolling to ND0612H-012) must satisfy all of the following criteria:

- 1. Subject is able to, and has signed an Institutional Review Board/Ethics Committee (IRB/EC)-approved informed consent form (ICF).
- 2. Subject has completed the treatment period of study ND0612H-006 not more than one month prior to enrolling in ND0612H-012.
- 3. Willing and able to administer the SC infusion alone or with the assistance of a study partner and able to comply with the study specific procedures.

To be eligible for study entry subjects in **Cohort 2** (ND0612 naïve subjects and subjects who completed treatment in a ND0612 clinical study more than one month before screening) must satisfy all of the following criteria:

- 1. Male and female PD subjects of any race aged at least 30 years who sign an IRB/EC-approved ICF.
- 2. PD diagnosis consistent with the UK Brain Bank Criteria.
- 3. Modified Hoehn & Yahr scale in "ON" state of stage ≤ 3 .
- 4. Taking at least 4 doses/day of LD/DDI (or at least 3 doses/day of Rytary) and taking, or have attempted to take, at least one other PD treatment for at least 30 days.
- 5. Subjects must be stable on their anti-PD medications for at least 30 days before Day 1.
- 6. Subjects may have had prior exposure to SC apomorphine injections/infusion but must have stopped continuous apomorphine administration at least 4 weeks before the screening visit. Treatment with apomorphine is prohibited during the entire ND0612 treatment period.
- 7. Must have a minimum of 2 hrs of "OFF" time per day with predictable early morning "OFF" periods as estimated by the subject.
- 8. Must have predictable and well defined early morning "OFF" periods with a good response to LD for treatment of the early morning "OFF" in the judgement of the investigator.
- 9. Mini Mental State Examination (MMSE) score ≥ 26 .

- 10. No clinically significant medical, psychiatric or laboratory abnormalities which the investigator judges would be unsafe or non-compliant in the study.

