11.1.4.3.1 Definition of Efficacy Endpoints

The exploratory efficacy endpoints assessed for 12 months of treatment are:

- Change in daily "ON" time without troublesome dyskinesia (defined as the sum of "ON" time without dyskinesia and "ON" time with non-troublesome dyskinesia) from Baseline to the 12-month visit based on home "ON/OFF" diaries.
- Change in daily "OFF" time from Baseline to the 12-month visit, based on home "ON/OFF" diaries.
- Change in total daily dose of oral LD/DDI from Baseline to the 12-month visit.
- Proportion of responders at the 12-month visit based on daily "OFF" time recorded in home "ON/OFF" diaries. A responder is defined as a subject that experiences ≥50% reduction in "OFF" time from Baseline.
- Change in daily "ON" time with troublesome dyskinesia in a subset of subjects who had more than 1 hour of troublesome dyskinesia at Baseline, based on home "ON/OFF" diaries from Baseline to the 12-month visit.

- Change in PDQ-39 scores from Baseline to the 12-month visit.
- Change in EQ-5D-5L scores from Baseline to the 12-month visit.
- Change in UPDRS Part II (ADL) from Baseline to the 12-month visit.
- Change in CGI-Severity and CGI-Improvement from Baseline to the 12-month visit.
- Change in SGI-Improvement from Baseline to the 12-month visit.
- Change in PDSS total score from Baseline to the 12-month visit
- Change in UPDRS Part III (motor score) from Baseline to the 12-month visit.
- Change from baseline to month 12 in percentage of "OFF" time and percentage of 'Good' ON during the first 3 hours since the subject is awake after 06:00 (6 am)
- Change from baseline to month 12 in ND0612 total dose
- Proportion of patients who reduced ND0612 total dose at any time during the study

The first efficacy endpoint of the change from Baseline to Month 12 in daily "ON" time without troublesome dyskinesia will be based on subject diary data. This will be a within group analysis for each treatment regimen. Subjects will provide data on daily "ON" and "OFF" time for the 2 days prior to the following visits: Baseline (Cohort 2 only), Months 1, 3, 6, 9, and 12 and the Early termination visit (if applicable) and additionally at Months 18, 24, 30, and 36 of the extension period. Subjects in Cohort 1, will be excluded from this analysis.

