1. PREFACE

This Statistical Analysis Plan (SAP) describes the planned analysis and reporting for NeuroDerm clinical trial ND0612H-012 (A multicenter, international, open-label, safety study of ND0612, a solution of levodopa/carbidopa delivered via a pump system as a continuous subcutaneous infusion in subjects with advanced Parkinson's Disease (BeyoND)), and was written in accordance with SOP 002 - Statistical Analysis Plan (NStat – [REDACTED] Procedure). The structure and content of this SAP provides sufficient details to meet the requirements identified by the FDA and International Conference on Harmonization of Technical Requirements for Registration of Pharmaceuticals for Human Use (ICH): E9 Guidance on Statistical Principles in Clinical Trials. All work planned and reported for this SAP will follow internationally accepted guidelines, published by the American Statistical Association, and the Royal Statistical Society, for statistical practice.

The following documents were reviewed in preparation of this SAP:

- Clinical Study Protocol ND0612H-012 Version 9.0 (global Amendment 8): issued on, July 11th 2019
- Case report form (CRF) for ND0612H-012
- ICH E9 Guidance on Statistical Principles for Clinical Trials.
- ICH E3 Structure and Content of Clinical Study Reports (CSRs)

This SAP describes the statistical analyses as it is foreseen before final database lock. The SAP will serve as a complement to the study protocol and supersedes it in case of differences between the SAP and the statistical sections of the protocol. In case of major differences, e.g. changes in the analysis related to the primary endpoint, a protocol amendment will be considered. The SAP may be updated during the study conduct and will be finalized before final database lock.

Based on FDA correspondences dated 27th of March 2019, Neuroderm was advised to focus its safety analysis on AE of Special Interest (AESI), specifically for Infusion Site Skin Reactions (ISR's). In addition, all cases of hypersensitivity reactions (e.g., diffuse skin rash, anaphylaxis and angioedema) should be considered AESI. Cases of Polyneuropathy were also considered as AESI.

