- 3.2.3.4.** Change from baseline to month 12 in percentage of “OFF” time during the first 3 hours since the subject is awake after 06:00 (6 am), based on subject’s “ON/OFF” diary assessments on the 3 consecutive days before the visit.
- Subject will be declared as ‘awake’ if found not ‘asleep’ for at least 2 hours after 06:00 (6 am)
 - This endpoint will be derived similarly as the daily “ON time without troublesome dyskinesia in 3.2.3.1. However, only data recorded after 06:00 (6 am) will be used for derivation. At least 5 out of 6 half-hour periods (3 hours) are required to be completed, in order to classify a diary day as valid.
- 3.2.3.5.** Change in total ND0612 total dose from baseline to month 12
- 3.2.3.6.** Proportions of patients who reduced their total ND0612 total dose during 12 month of treatment
- 3.2.3.7.** Proportion of responders at the 12-month visit based on daily “OFF” time recorded in "ON/OFF" diaries. A responder is defined as a subject that experiences $\geq 50\%$ reduction in “OFF” time from Baseline.
- The daily “OFF” time will be calculated as defined in 3.2.3.2. The percentage reduction will be calculated as $(OFF_{\text{Month 12}} - OFF_{\text{baseline}}) / OFF_{\text{baseline}} * 100$. The subjects will be dichotomized as having a percentage reduction of $\geq 50\%$ versus a reduction of $< 50\%$. The patients with missing “OFF” time will be imputed with last available ‘OFF’ time value. .
- 3.2.3.8.** Change in daily “ON” time with troublesome dyskinesia in a subset of subjects who had more than 1 hour of troublesome dyskinesia at Baseline based on home "ON/OFF" diaries from Baseline to the 12-month visit.
- The daily “ON” time with troublesome dyskinesia will be derived similarly as the daily “ON time without troublesome dyskinesia in 3.2.3.1.
- 3.2.3.9.** Change in PDQ-39 summary index and the 8 dimension scores from Baseline to the 12 month visit
- The PDQ-39 questionnaire provides scores on eight dimensions as outlined below:

- mobility (10 items, #1 to 10)
- activities of daily living (6 items, #11 to 16)
- emotional well-being (6 items, #17 to 22)
- stigma (4 items, #23 to 26)
- social support (3 items, #27 to 29)
- cognitions (4 items, #30 to 33)
- communication (3 items, #34 to 36)
- bodily discomfort (3 items, #37 to 39).

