8. EFFICACY

8.1. General

For the efficacy endpoints, continuous data will be summarized at each protocol scheduled visit, by treatment regimen, using summary statistics. Actual values and changes from baseline will be presented. All categorical endpoints will be summarized at each protocol scheduled visit, by treatment regimen, using frequency tabulations.

As the primary and secondary purpose of this study is to explore the 2 treatment regimens with regards to safety and efficacy and not to perform confirmatory analyses comparing the treatment regimens, there will be no formal hypothesis testing performed and adjustments for multiplicity are not required.

The analyses of the efficacy data will focus on estimating the changes from baseline of the present study for cohort 2 and from baseline of 006 study for cohort 1. Cohort 1 and Cohort 2 will be analyzed separately and combined. Data from Cohort 2 will be summarized by treatment group (Regimen 1 or Regimen 3), i.e. the summaries of efficacy data will include the following groups: Cohort 1/Regimen 1, Cohort 2/Regimen 1 and Cohort 2/Regimen 3. For the combined cohort analysis Regimen 1 and Regimen 3. The mITT set will be used for all efficacy analyses.

Sensitivity analyses of efficacy data will be conducted by excluding the patients who were randomized to receive Regimen 2. These analyses will be done for the “ON” time without troublesome dyskinesia.

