8.2.3. Change in daily “ON” time without any dyskinesia (troublesome or non-troublesome) based on home "ON/OFF" diaries from Baseline to the 12-month visit.

The daily “ON” time without any dyskinesia will be analyzed similarly as the “GOOD ON” time replacing baseline “GOOD ON” time with baseline “ON” time without any dyskinesia as covariate.

8.2.4. Proportion of responders at the 12-month visit based on daily “OFF” time recorded in home "ON/OFF" diaries. A responder is defined as a subject that experiences $\geq 50\%$ reduction in “OFF” time from Baseline.

The proportion of patients fulfilling the response criterion will be tabulated by visit. In addition, cumulative percentage of patients with reduction in “OFF” time normalized to a 16-hour waking day will be plotted as a function of percent reduction in “OFF” time from baseline to Month 12..

8.2.5. Change in daily “ON” time with troublesome dyskinesia in a subset of subjects who had more than 1 hour of troublesome dyskinesia at Baseline based on home “ON/OFF” diaries from Baseline to the 12-month visit.

The daily “ON” time with troublesome dyskinesia in the subset of subjects who had more than 1 hour of troublesome dyskinesia at Baseline will be analyzed similarly as the “GOOD ON” time replacing baseline “GOOD ON” time with baseline “ON” time with troublesome dyskinesia as covariate.

8.2.6. Change in PDQ-39 summary index and the 8 dimension scores from Baseline to the 12-month visit

The PDQ-39 summary index and the 8 dimension scores will be analyzed similarly as the “GOOD ON” time replacing baseline “GOOD ON” time with baseline PDQ-39 as covariate.

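### The OFF-time responder formula in SAP 3.2.3.7 has the wrong sign: coded as printed, it counts rises of 50% or more as responses

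*SAP*

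**What the plan says.** The endpoint is the proportion of responders at Month 12, based on diary OFF time. The protocol gives it in words only. Section 11.1.4.3.1 reads "A responder is defined as a subject that experiences" a reduction in OFF time of 50% or more from Baseline. SAP 3.2.3.7 repeats that definition and the heading of SAP 8.2.4 carries it too. SAP 2.3 describes the same outcome as an improvement of at least 50%.

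SAP 3.2.3.7 then adds the computation: "The percentage reduction will be calculated as" (OFF Month 12 − OFF baseline) / OFF baseline × 100. The next sentence applies the cut-off: "The subjects will be dichotomized as having a percentage reduction of" 50% or more, against a reduction below 50%.

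SAP 8.2.4 describes two outputs. For the table, "The proportion of patients fulfilling the response criterion will be tabulated by visit". For the plot, the cumulative percentage of patients "will be plotted as a function of percent reduction in" OFF time from baseline to Month 12. It gives no formula of its own.

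**The concern.** A quantity labelled a reduction should be positive when OFF time falls. The printed numerator is Month 12 minus baseline, so it is negative when OFF time falls and positive when it rises. With a cut-off of 50 or more, the formula and the worded definition in the same item point in opposite directions.

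This is the only computational instruction for the endpoint. Neither document gives an absolute value, a reversed sign or a cut-off at −50%. SAP 1.2 assigns the programming to a contract research organization, so the formula is what the programmers receive. Literal coding would put subjects who clearly worsened in the responder table and leave out everyone who improved. The cumulative plot would be reversed if the same quantity were used for it.

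**Working it through.** **Inputs.** The formula, the cut-off and the worded definition come from SAP 3.2.3.7. Normalization of OFF time to 16 waking hours comes from SAP 3.2.3.1, through 3.2.3.2.

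**Algebra.** Let B be baseline OFF time (B > 0) and M be Month 12 OFF time.

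- Printed rule: (M − B)/B × 100 ≥ 50, which is M ≥ 1.5 B.
- Worded rule: (B − M)/B × 100 ≥ 50, which is M ≤ 0.5 B.

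No M satisfies both when B > 0.

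**Worked cases.**

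| B to M (h) | Printed formula | Printed rule | Reversed numerator | Worded rule |
|---|---|---|---|---|
| 6 to 0 | −100% | non-responder | +100% | responder |
| 6 to 2 | −66.7% | non-responder | +66.7% | responder |
| 6 to 3 | −50% | non-responder | +50% | responder |
| 2 to 1 | −50% | non-responder | +50% | responder |
| 6 to 4 | −33.3% | non-responder | +33.3% | non-responder |
| 6 to 9 | +50% | responder | −50% | non-responder |
| 2 to 3 | +50% | responder | −50% | non-responder |

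**Grid check.** All pairs on a half-hour grid from 0 to 16 h with B > 0 were evaluated. For improving pairs the printed value runs from −100 to −3.125, so none reaches 50. Every pair that reaches 50 has M ≥ 1.5 B. No pair is a responder under both rules.

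**Ceiling.** With OFF time capped at 16 h, the printed rule needs 1.5 B ≤ 16, so B ≤ 16/1.5 = 10.67 h. A subject above that baseline could never be a responder as printed.

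**Illustration of size.** The documents give no OFF-time means or SDs, so every input here is assumed:

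- baseline normal with mean 5 or 6 h and SD 2, clipped to 2–16 h;
- change normal with mean −1, −2 or −3 h and SD 2 or 3;
- Month 12 clipped to 0–16 h;
- 12 scenarios of 400,000 simulated subjects each.

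The printed rule gives 0.3–13.1% responders and the worded rule 18.3–58.6%. The gap within a scenario is 14.7 to 58.0 percentage points. With the baseline floor at 0.5 h the ranges are 0.3–13.4% and 18.7–58.9%. Repeat runs with the 2 h floor agree to within about 0.5 percentage point.

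**Baseline of 0.** The ratio is undefined at B = 0, and reversing the numerator does not change that. Protocol 8.3.2, Cohort 2 criterion 7, asks for at least 2 h of OFF time per day with early morning OFF "periods as estimated by the subject", which is not a diary value. SAP 4.4 requires baseline diary data for the Cohort 2 mITT Set but sets no minimum OFF time. How often a diary baseline of 0 would occur cannot be judged from the documents.

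**The case against.** The strongest reply is that the surrounding words already settle the direction. The responder definition and the dichotomization sentence both speak of a reduction, and a rise from 6 h to 9 h is not one. A careful programmer would read −50% as a 50% reduction. Literal coding would also disagree visibly with the OFF-time model in SAP 8.2.2. On this view the fault is an internal inconsistency of label and sign. This stands as a reason to expect the error to be caught, but it does not make the formula right.

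The stakes are also low. The endpoint is exploratory and tabulated descriptively, and SAP 8.1 says "there will be no formal hypothesis testing performed and adjustments for multiplicity are not required". That is accepted.

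SAP section 1 says that the SAP "supersedes it in case of differences between the SAP and the statistical sections of the protocol". It can be answered that the SAP's own words match the protocol's, so this clause does not by itself install the wrong rule. That is fair. The clause does mean that the protocol's correct wording is no safeguard and that the repair belongs in the SAP.

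SAP 8.2.4 does not cite the formula, and the formula names Month 12 only. Its use for the by-visit table and the plot is therefore an inference, though no other formula is available.

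The zero-baseline point is independent of the sign. Criterion 8, which asks for well-defined early morning OFF in the investigator's judgement, makes a zero less likely. SAP 5.1 uses non-missing observations as the visit denominator, so an undefined ratio might simply drop out. It is a missing detail and carries little weight here.

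**Conclusion.** The concern holds. The formula printed in SAP 3.2.3.7 is percentage change under the label of percentage reduction. With the stated cut-off it selects the opposite of the defined responders. This rests on algebra alone and needs no assumption beyond a baseline above 0. The operands are complete and legible, so it is not an artefact of text extraction.

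The practical size depends on whether the formula is coded literally. If it is, the responder set is entirely wrong. The simulated gap of roughly 15 to 58 points only illustrates this under assumed inputs and is not an expected bias. If the programmers follow the words, nothing changes. The primary safety analysis is unaffected either way. This should be corrected before programming, but it does not threaten the study's main conclusions.

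**What to change.** In SAP 3.2.3.7, define percentage reduction at each visit as (OFF baseline − OFF visit) / OFF baseline × 100, with a responder at 50% or more. Keeping the printed expression, calling it percentage change and setting the cut-off at −50% or below would be equivalent. State that the same definition governs the by-visit responder table and the cumulative plot in SAP 8.2.4.

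Add one sentence for a diary baseline OFF time of 0, for example leaving such subjects out of the denominator and reporting how many there are.

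The cost is one corrected line and one added sentence. No new data, visits or analyses are needed.

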3.2.3.10. Change in EQ-5D-5L scores from Baseline to the 12 month visit

- The EQ-5D is a utility scale consisting of three components: health state dimensions, health state thermometer scale and health state index.
 - The health state dimensions will be described by the 5 dimensions of the EQ-5D (mobility, self-care, usual activities, pain/discomfort and anxiety/depression). Each dimension has 5 response choices, listed in order of increasing severity.
 - The health state thermometer scale asks respondents to rate their present health status on a 0 to 100 visual analog scale (VAS). The change from Baseline visit to the 12 month visit in the VAS scores will be evaluated.
 - The health state index score will be calculated using the dimension scores from the 5 dimensions, ranging between 1.0 (best imaginable health) and -0.594 (worst imaginable health). The change from Baseline visit to the 12 month visit

in the health state index score will be evaluated.

3.2.3.11. Change in UPDRS Part II (ADL) from Baseline to the 12 month visit.

- The UPDRS part II (ADL) score will be calculated as the sum of the individual items 5-17. Missing individual items will not be imputed. If there is at least 1 missing item, the corresponding sum score will be set as missing.

3.2.3.12. Change in CGI-Severity (CGI-S) and CGI-Improvement (CGI-I) from Baseline to the 12 month visit

- The CGI-I scores will be categorized as improvements (very much improved, much improved, minimally improved) or non-improvements (no change, minimally worse, much worse, very much worse). For descriptive statistics, in case the CGI-I score is missing (or “Not assessed”) but the visit in question was done, the last non missing available data will be used for incomplete data.
- The changes from Baseline in CGI-S score will be categorized as improvements if the value at the visit in question is better than the baseline value. If the value at the visit in question is same or worse than the baseline value, the change is categorized as a non-improvement. “Normal, not at all ill” is considered as the best value and “Among the most extremely ill” the worst. For descriptive statistics, in case the post-baseline CGI-S score is recorded as “Not assessed”, but the visit in question was done, the last non missing available data will be used for incomplete data. In case the baseline value is missing or recorded as “Not assessed”, the change will be set as missing.

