5. GENERAL ASPECTS FOR DATA ANALYSIS

5.1. General Methods

All data from all patients entered into the study will be included in patient data listings. The listings will be sorted by center, and patient number (and by visit, if applicable).

The data will be summarized using either descriptive statistics (number of non-missing observations, mean, median, SD, standard error of the mean (SEM), minimum and maximum) for continuous data or frequency counts and percentages for categorical data. For visit-specific data, the number of subjects with non-missing observations at the visit in question will be used as the denominator for percent calculations. Unknown, Not Done, Not Applicable and other classifications of missing data will not be considered.

The summaries will be broken down by treatment regimen (Regimen 1, Regimen 3) and by visit, as applicable. For demographic and other baseline characteristics and selected safety data, an overall column will be displayed in addition to the data broken down by the treatment regimen. Unscheduled or repeated assessments will not be included in summary tables but will be included in listings.

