5.4. Handling Withdrawals and Missing Data

In general, there will be no imputation for missing data, unless otherwise specified

The primary objective of this study is safety. Safety data will not be subject to any imputation and will be summarized on an observed case basis. For the analysis of the AEs, the incomplete follow-up will be taken into account by summarizing the data as annualized rates in addition to the

frequency counts and percentages. The analysis of the annualized rates takes into account the actual duration of the exposure to the study treatment.

For the efficacy endpoint, the missing data will be handled as follows:

- For patients who withdraw from the study, data at the early termination visit will be excluded from the by-visit summaries but will be included in the closest visit in case this visit was missing.
- For the continuous efficacy endpoints, likelihood-based modeling approach will be used to handle incomplete data. For this purpose, Mixed Model for Repeated Measures (MMRM) will be applied, see section 8.2.1.
- For categorical efficacy endpoints, the last non missing available data will be used for incomplete data.

All withdrawals will be included in all analyses up to the time of withdrawal. Subjects who are withdrawn prematurely from study drug and/or the study will be included in all analyses regardless of the duration of treatment.

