7.4. Tolerability and Treatment Compliance

7.4.1. Tolerability

Tolerability will be assessed based on percentage of subjects that complete the 12-month treatment period of the study and the percentage of subjects who discontinue from the 12-month treatment period due to a TEAE. Time (days) from enrolment to discontinuation will be illustrated as Kaplan-Meier curves by treatment regimen. Patients who complete the study will be right censored at the date of last dose of study treatment during the 12-month study period. Time to discontinuation will also be explored by recruitment wave 1 and 2 following corrective actions for patients' retention.

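### The Month 12 OFF-time responder rate carries the last diary forward without limit, so a Cohort 2 subject who stopped ND0612 early can be counted as a Month 12 responder

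*SAP*

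**What the plan says.** **The endpoint.** SAP 3.2.3.7 is titled as a proportion at the 12-month visit. "A responder is defined as a subject that experiences" a fall in OFF time of at least 50% from baseline. Patients with missing OFF "time will be imputed with last available" OFF value.

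**The default.** SAP 5.4 says: "For categorical efficacy endpoints, the last non missing available data will be used for incomplete data". The same section keeps subjects who withdraw early from drug or study: they "will be included in all analyses regardless of the duration of treatment". Early-termination data "will be included in the closest visit in case this visit was missing".

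**The analysis set.** SAP 4.4 admits a Cohort 2 subject to the mITT set on a baseline diary plus one valid post-baseline measurement. Cohort 1 is left out of the diary analyses (SAP 3.2.3).

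**The analysis.** SAP 8.2.4 tabulates responders by visit and adds a cumulative plot of percent reduction to Month 12. It plans neither an observed-case nor a non-responder version. Continuous OFF time, by contrast, goes into a mixed model without imputation (SAP 8.2.1 and 8.2.2).

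**CGI and SGI.** For CGI-I and CGI-S, SAP 3.2.3.12 carries a value forward only if the score is missing "but the visit in question was done, the last non missing available data will be used for incomplete data". SAP 3.2.3.13 derives SGI-I in the same way. SAP 5.1 adds that for visit-specific data "the number of subjects with non-missing observations at the visit in question will be used as the denominator for percent calculations".

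**The concern.** A reader will take a responder rate labelled Month 12 as the share of subjects who, a year on, have halved their OFF time on ND0612. Under the rule as written it is instead the share whose last recorded diary met the criterion, whenever that diary was kept.

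A subject who terminates early returns the pump and is prescribed commercial oral levodopa (Protocol 9.2.8). The carried value then describes a treatment the subject no longer receives. Infusion-site reaction is one of the listed reasons for withdrawal (Protocol 8.3.4), so some carried values may come from subjects who could not tolerate the infusion.

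This matters because staying on treatment is part of the primary tolerability assessment, and because retention was evidently a live issue: "Time to discontinuation will also be explored by recruitment wave 1 and 2 following corrective actions" for retention (SAP 7.4.1). If the responder rate is quoted as durable benefit, it will include people who had left treatment, and no planned table shows how many.

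**Working it through.** The plan states no responder rate, dropout rate or power for this endpoint, so there is no figure of its own to reproduce. The check follows the rules for one subject and then gives the size of the effect in general terms.

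**One subject (assumed diaries).** Baseline OFF is 6.0 h and Month 1 OFF is 2.5 h. The subject then withdraws for an infusion-site reaction and keeps no later diary.
1. Baseline plus one valid post-baseline diary puts the subject in the Cohort 2 mITT set (SAP 4.4).
2. Month 12 OFF time is missing, so 2.5 h is carried forward (SAP 3.2.3.7).
3. Change = (2.5 − 6.0)/6.0 × 100 = −58.3%. Read as a reduction, 58.3% exceeds 50%.
4. The subject is a Month 12 responder after about 11 months off the infusion.

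An early-termination diary would replace the Month 1 value as the last one available. It is collected only if possible (Protocol 10.2.1.1), it reflects status around stopping, and it is then carried forward in turn.

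**In general.** Let d be the share of the Cohort 2 mITT set who stopped before Month 12 and have no Month 12 diary, r the share of those whose last diary met the criterion, and c the responder rate in completers. Suppose every completer has a valid Month 12 diary.
- Carry-forward rate = (1 − d)c + d·r
- Rate with stoppers as non-responders = (1 − d)c
- Observed-case rate = c
- Carry-forward minus non-responder rate = d·r, never negative
- Carry-forward minus observed-case rate = d(r − c), either sign

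All values of d, c and r below are assumptions.

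| d | c | r | Carry-forward | Stoppers as non-responders | Gap (points) | Carry-forward minus observed (points) |
|---|---|---|---|---|---|---|
| 10% | 50% | 20% | 47.0% | 45.0% | 2.0 | −3.0 |
| 20% | 50% | 35% | 47.0% | 40.0% | 7.0 | −3.0 |
| 30% | 50% | 35% | 45.5% | 35.0% | 10.5 | −4.5 |
| 40% | 50% | 50% | 50.0% | 30.0% | 20.0 | 0.0 |
| 40% | 40% | 50% | 44.0% | 24.0% | 20.0 | +4.0 |

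**In subjects.** Protocol 11.2 plans about 210 treated subjects with at most 36 in Cohort 1, leaving about 210 − 36 = 174 in Cohort 2. If all were in the mITT set, the gap would be about 174 × 0.02 = 3 to 174 × 0.20 = 35 subjects. SAP 3.3 gives a smaller total (120–170), for which the counts would be lower.

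**Outside the calculation.** Treated Cohort 2 subjects who stop before any valid post-baseline diary are not in the mITT set. They leave both numerator and denominator and are not counted as failures.

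**The case against.** The strongest case against has four parts.

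**The comparator is a choice.** The d × r gap is measured against a definition in which stopping counts as failure. It is not bias against a known truth. This stands. A reader might infer that carry-forward inflates the rate whatever it is compared with, and the table shows otherwise: in three of five rows it lies below the observed-case figure. What remains is that the plan labels the result as Month 12 response, shows only one version, and leaves the reader unable to see the others.

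**The endpoint is minor and tolerability is reported elsewhere.** Efficacy is exploratory, the study is open-label, and no formal hypothesis testing is planned. Completion, discontinuation due to a TEAE and Kaplan-Meier time to discontinuation are reported directly (SAP 7.4.1), with reasons for discontinuation in SAP 6.2. This stands, and it rules out any claim that a primary conclusion is at risk.

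**The early-termination diary may catch loss of effect.** Where it exists, it may. It is not guaranteed, and a subject who stops for intolerance may still be responding at that point.

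**The rules do not all collide in one table.** A reader might infer that SAP 3.2.3.12, 5.4 and 5.1 give three competing percentages for OFF responders. They do not: 3.2.3.12 concerns CGI (and SGI-I through 3.2.3.13), while 3.2.3.7 and 5.4 agree for OFF time. For CGI and SGI, the specific rule can be read as narrowing the default, but the SAP does not say so. Whether an imputed value counts as non-missing under 5.1 is open for every endpoint that uses carry-forward.

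A reader might also infer that dropout differs between regimens and distorts their comparison. The documents plan curves by regimen and by recruitment wave but report no difference.

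**Conclusion.** The point holds for this endpoint. As written, SAP 3.2.3.7 and 5.4 allow a Cohort 2 mITT subject who stopped ND0612 early to be counted as a Month 12 responder on an on-infusion diary, and no planned analysis shows the effect.

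Against counting stoppers as non-responders, the rate is higher by d × r: 2–20 percentage points under assumed d of 10–40% and r of 20–50%. Neither quantity is in the documents, so this range illustrates the size and does not predict it. Against observed cases, the direction depends on whether r exceeds the completer rate.

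The consequence is confined to how one exploratory, descriptive table is read. The primary safety and tolerability results do not change. The CGI and SGI wording is a related but separate clarification.

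**What to change.** **OFF responders (SAP 3.2.3.7, 5.4 and 8.2.4)**
- Tabulate the Month 12 responder rate in the Cohort 2 mITT denominator, with subjects who stopped ND0612 before Month 12 counted as non-responders.
- Count subjects still on ND0612 without a valid Month 12 diary as non-responders too, and report how many there are, so that the effect of this conservative choice is visible.
- State the number of treated Cohort 2 subjects excluded from the mITT set for lack of a valid post-baseline diary.
- Show the observed-case percentage beside the main figure, and keep carry-forward only as a sensitivity figure.

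**CGI-I, CGI-S and SGI-I**
- State that the rule in SAP 3.2.3.12 overrides the default in 5.4.
- State whether imputed values enter the denominator defined in 5.1.

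**Cost.** SAP wording and one extra table column, using data already planned for collection. The headline responder figure becomes less favourable.
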